### **12.3.1 Premature Discontinuation Description**

For each premature discontinuation, the following parameters will be listed: participant number, dates of start and end of treatment, and the reason of premature discontinuation.

### **12.3.2 Safety**

For adverse events, a descriptive analysis will be given. Adverse events will be presented in a frequency table by category and treatment. Furthermore, description, frequency, severity, and causality will be reported for each adverse event.

Continuous safety parameters (e.g. hematology, clinical chemistry, heart rate and blood pressure, urine specific gravity) will be summarized using a table including mean, standard deviation, median, minimum value, and maximum value for each measurement point. These will be compared to normal clinical ranges and any abnormalities will be discussed.

Protocol 20BWHM:

A randomized, double-blind, placebo-controlled study to investigate the effects of a *Bifidobacterium breve* strain on fat loss in healthy adults

Categorical safety parameters (e.g. incidence of adverse events and urinalysis (microscopy, glucose, ketones, blood, protein, colour)) will be summarized as counts and percentages. The denominator for each percentage will be the number of subjects within the study group for that visit/week unless otherwise specified. Possible differences between groups will be assessed by using the two-tailed Chi-squared or Fisher's exact test, as appropriate.

## **12.4 Protocol Deviation Description**

Protocol deviations will be listed in the final study report.

## **12.5 Protocol Amendments**

Once the protocol has been approved by the IRB and Health Canada, any changes to the protocol must be documented in the form of an amendment. All amendments will be documented in the final study report.

## **13 DATA COLLECTION AND STORAGE**

All data collection and record storage will be done in compliance with ICH GCP Guidelines and applicable local regulatory guidelines.

## **14 ETHICAL ASPECTS OF THE STUDY**

This study will be conducted with the highest respect for the individual participants (i.e., participants) according to the protocol, the ethical principles that have their origin in the Declaration of Helsinki, and the ICH Harmonised Tripartite Guideline for GCP.

### **14.1 IRB Approval**

KGK Science Inc. will supply relevant documents for submission to an IRB for the protocol's review and approval. The following must be submitted to the IRB: this protocol, a copy of the informed consent form, and, if applicable, volunteer recruitment materials and/or advertisements and other documents required by all applicable laws and regulations. The IRB's written approval of the protocol and volunteer informed consent must be obtained before commencement of the study. The IRB approval must refer to the study by exact protocol title, number, and version date; identify versions of other documents (e.g., informed consent form) reviewed; and state the approval date.

Protocol 20BWHM:

A randomized, double-blind, placebo-controlled study to investigate the effects of a *Bifidobacterium breve* strain on fat loss in healthy adults

KGK must adhere to all requirements stipulated by the IRB. This may include notification to the IRB regarding protocol amendments, updates to the informed consent form, recruitment materials intended for viewing by volunteers, local safety reporting requirements and submission of the investigator's annual/final status report to the IRB.

#### **14.2    Volunteer Information and Informed Consent**

Written consent documents will embody the elements of informed consent as described in the declaration of Helsinki and the ICH Guidelines for GCP and will be in accordance with all applicable laws and regulations. The informed consent form describes the planned and permitted uses, transfers, and disclosures of the volunteer's personal and personal health information for purposes of conducting the study. The informed consent form further explains the nature of the study, its objectives, and potential risks and benefits, as well as the date informed consent is obtained. The informed consent form will detail the requirements of the volunteer and the fact that he or she is free to withdraw at any time without giving a reason and without prejudice to his or her further medical care.

#### **14.3    Potential Risks and Procedures to Minimize Risk**

All potential risks are disclosed to study participants prior to their participation. The potential risks associated with this study include venipuncture and the associated risks. Risks associated with venipuncture include pain, bruising, and infection at the site. Alcohol swabs and proper venipuncture procedures will be followed to minimize the risk of infection.

### **15    QUALITY ASSURANCE AND QUALITY CONTROL**

#### **15.1    Auditing**

All materials used in clinical studies are subjected to quality control. Quality assurance audits may be performed by the sponsor or any health authority during the course of the study or after its completion.

The Investigator agrees to comply with the sponsor and regulatory requirements in terms of auditing of the study. This includes access to the source documents for source data verification.

#### **15.2    Monitoring**

An initiation meeting will be conducted by the sponsor or an approved representative (CRO). At this meeting, the protocol and logistical aspects of the study will be reviewed with the Investigator and all study staff.

Protocol 20BWHM:

A randomized, double-blind, placebo-controlled study to investigate the effects of a *Bifidobacterium breve* strain on fat loss in healthy adults

Source documents will be reviewed to ensure that all items have been completed and that the data provided are accurate and obtained in the manner specified in the protocol. The participant files will be reviewed to confirm that:

1. Informed consent was obtained and documented
2. Enrolled participants fulfilled all inclusion criteria and did not meet any exclusion criteria;
3. AE/SAE reporting has been performed as applicable
4. Study visits have been conducted as per protocol and information has been recorded in the appropriate place in the source document
5. The study product is being stored correctly and an accurate record of its dispensation to the study participants is being maintained (accountability)

Incorrect, inappropriate, or illegible entries in the participant files will be returned to the Investigator or designee for correction. No data disclosing the identity of participants will leave the study center. The Investigator and any designees will maintain confidentiality of all participant records.

The Investigator will permit trial-related monitoring, audits, IRB/IEC review, and regulatory inspections and will allow direct access to source data and documents for these purposes.

### **15.3 Data Management**

Data required for the analysis will be acquired from source documentation (including laboratory reports) and entered into Open Clinica Enterprise Version study instance designed specifically for this study. The two instances for the database would be created, test instance and production instance. A UAT (User Acceptance Testing) of the database would be performed in the test instance and then moved to the production instance. A password protected user id's will be created which would give access to the limited authorized personnel. Only properly trained Data management staff will be granted access to perform database designing, according to SOP - Designing Database in Open Clinica Enterprise Version and SOP - Creating user in Open Clinica Enterprise Version. A study-specific Data Management Plan will be generated after the finalization of the database.

The standard data validation and edit checks would be performed on the production instance of the study by designing study specific rules and restrictions as defined in the eCRF. The discrepancies will be queried and managed according to the SOP - Discrepancy Management SOP in Open Clinica Enterprise Version. Data tables will be created, queried and exported during and at the end of study using PostgreSQL tool (pgadminIII 9.5) and MS Access.

For Statistical analysis, the validated soft-lock copy of the blinded study database will be sent to the Statistician to perform the analysis. The study database would be a read-only file to ascertain changes in the data are not made during or after the analysis.

High safety standards for the transfer and storage of study data are guaranteed by the use of technologies such as password protection, firewalls and periodic backup to protect stored data.

Protocol 20BWHM:

A randomized, double-blind, placebo-controlled study to investigate the effects of a *Bifidobacterium breve* strain on fat loss in healthy adults

All study data is archived for a period not less than 25 years from the date of completion of the study in accordance with Health Canada regulatory requirements.

## 17 APPENDICES

### 17.1 Appendix I: Probiotic and Prebiotic Foods to Avoid

## Dietary Guidelines

Please use the following guidelines to help you make meal and snack choices between study visits that are appropriate for the study.

***\*\*\* Please refrain from ingesting any foods or beverages with live bacteria or yeast present during the course of the trial. \*\*\****

#### **Supplements to Avoid:**

Probiotic supplements – any food, capsule or orally administered product containing live bacteria or yeast, often labeled as bacteria or yeast fermentation products (such as: *Lactobacillus*, *Bifidobacteria*, *Bacillus*, *saccharomyces*)

Prebiotic supplements – any orally administered product with the specific function of increasing bacterial populations.

#### **Foods to Avoid:**

- Yoghurt
- Naturally fermented cabbage (including but not limited to sauerkraut, kimchi)
- Naturally fermented pickles, cucumbers, and other vegetables
- Fermented soy products (including but not limited to tempeh, miso, natto)
- Uncooked buttermilk products
- Soft cheeses, live culture cheeses (including but not limited to blue cheese, gouda, goat cheese)
- Cold or uncooked sausage products
- Foods marketed as “Probiotic” or “Live Culture”

#### **Beverages to Avoid:**

- Kefir
- Kombucha
- Apple cider vinegar
- Lambic beers
- Sour ales
- Wheat beers
- Other beverages labeled as probiotic

Protocol 20BWHM:

A randomized, double-blind, placebo-controlled study to investigate the effects of a *Bifidobacterium breve* strain on fat loss in healthy adults

**Foods to Limit:** (~2 servings per week)

- Onions, leeks, garlic
- Asparagus, artichokes, chicory root, dandelion greens

## 17.2 Appendix II: Daily Bowel Habits Diary with Bristol Stool Scale

Daily Bowel Habits Diary with Bristol Stool Scale will be completed every day by the participants.

Date:						
Comments/Therapies/Medication (dose, frequency, reason for use)/Changes in Health:						

For each bowel movement you experienced today record the time (in 24-hour format) for question 1 and circle Yes or No (Y/N) for questions 2-7.
 
For question 5 please refer to the Bristol Stool Scale and record the type that best describes the bowel movement.
 
If you do not have any bowel movements, circle 0 and complete question 2, 6 and 7.
						
	Bowel Movement Number					
	* If required, additional movements and details can be added to the back of the diary					
	0	1	2	3	4	5
1. Time of Bowel Movement (hh:mm)	N/A	____ : ____	____ : ____	____ : ____	____ : ____	____ : ____
2. Straining to start defecation?	Y / N or N/A	Y / N	Y / N	Y / N	Y / N	Y / N
3. Straining to stop defecation?	N/A	Y / N	Y / N	Y / N	Y / N	Y / N
4. Feeling of incomplete defecation?	N/A	Y / N	Y / N	Y / N	Y / N	Y / N
5. Bristol Stool Form Type (1-7) see below?	N/A					
6. Were laxatives, enemas or suppositories used in the 24 hours prior to the bowel movement?	Y / N	Y / N	Y / N	Y / N	Y / N	Y / N
7. For Females: Do you feel that your bowel movements today were affected by your menstrual cycle? Y / N						

### For Question 5 Bristol Stool Form Type (1-7)

Type 1 	Separate hard lumps, like nuts (hard to pass)	Type 3 	Like a sausage but with cracks on its surface	Type 5 	Soft blobs with clear-cut edges (passed easily)
Type 2 	Sausage-shaped but lumpy	Type 4 	Like a sausage or snake, smooth and soft	Type 6 	Fluffy pieces with ragged edges, a mushy stool
				Type 7 	Watery, no solid pieces. Entirely Liquid

### 17.3 Appendix III: Exercise Guidelines

Please use the following guidelines to help you select the type of exercise that is appropriate for this study

***\*\*\* Please ensure that you exercise 3 times per week for 20 minutes at a moderate intensity (can be in bouts of 5-10 minutes)\*\*\****

#### Examples of moderate and high-intensity exercise

Moderate-intensity Physical Activity	High-intensity Physical Activity
Activities elevate the heart rate and cause light sweating after about 10 minutes. Breathing is heavier than normal, but you can carry a conversation.	Activities elevate the heart rate substantially and cause significant sweating. You cannot carry a conversation due to heavy breathing.

 
• Brisk walking
 
• Bicycling (easy pace)
 
• Light to moderate workouts on gym equipment
 
• Water aerobics
 
• Swimming (leisure pace)
 
• Carrying moderate loads
 
• Participating in active games with children (eg. Hopscotch, dodgeball)
 
• Dancing (social)
 
	
 
• Running
 
• Bicycling (brisk pace)
 
• Swimming (fast pace)
 
• Carrying heavy loads
 
• Playing competitive sports
 
• Cross-country skiing
 
• Dancing (competitive)
 

## 2. OVERVIEW AND ENDPOINTS

The objective of this study is to investigate the effect of *Bifidobacterium breve* on fat loss in healthy adults.

### Primary Outcome

The difference in change in fat loss from baseline (% or g), as assessed by Dual-Energy X-Ray Absorptiometry (DXA), between *B. breve* and placebo after 12 weeks of supplementation.

#### 2.1 Secondary Outcomes

The difference in change from baseline between *B. breve* and placebo in:

1. Body composition (weight, BMI, android/gynoid fat ratio, and muscle mass (% or g) as assessed by DXA after 12 weeks of supplementation
2. Waist circumference, hip circumference, and waist/hip circumference ratio after 6 and 12 weeks of supplementation
3. Lipid profile (total cholesterol, HDL-cholesterol, LDL-cholesterol, triglycerides) after 12 weeks of supplementation
4. Biomarkers of glycemic control (fasting blood glucose, HbA1c, fasting insulin levels) after 12 weeks of supplementation
5. Liver markers (aspartate transaminase (AST), alanine aminotransferase (ALT), gamma-glutamyl transferase (GGT), and alkaline phosphatase (ALP)) after 12 weeks of supplementation
6. Frequency of bowel movements after 6 and 12 weeks of supplementation
7. Body composition (weight, BMI, total body fat (% or g), android fat (% or g), gynoid fat (% or g), android/gynoid fat ratio, and muscle mass (% or g) and waist circumference, hip circumference, and waist/hip circumference ratio) in participant groups classified by microbiota composition at week 0
8. Microbiota composition analysis

#### 2.2 Safety Outcomes

1. Incidence of pre-emergent and post-emergent adverse events
2. Vital signs (blood pressure (BP) and heart rate (HR)), respiratory rate, and temperature
3. Clinical chemistry (total bilirubin, creatinine, blood urea nitrogen (BUN), Na, K, Cl, Ca, Fe, Mg, phosphate, and estimated glomerular filtration rate (eGFR))
4. Hematology (white blood cell (WBC) count with differential (neutrophils, lymphocytes, monocytes, eosinophils, basophils), red blood cell (RBC) count, hemoglobin, hematocrit, platelet count, RBC indices (mean corpuscular volume (MCV), mean corpuscular hemoglobin (MCH), mean corpuscular hemoglobin concentration (MCHC), red cell distribution width (RDW), and mean platelet volume (MPV))
5. Urinalysis (microscopy, glucose, ketones, specific gravity, blood, protein, nitrite, leukocytes, colour, appearance urobilinogen/urine bilirubin, urine pH)

### 2.3 Exploratory analyses

1. Total body fat (%) change during the run-in period as assessed by bioelectrical impedance analysis (BIA)
2. Comparison of total body fat (%) as assessed by BIA and DXA at baseline

### 3. STUDY POPULATION

A total of three populations are defined for all summaries and analyses. Subjects who satisfy the inclusion/exclusion criteria will be classified in the designated populations:

- **The Safety Population** will consist of all participants who received any amount of either product and on whom any post-randomization safety information is available.
- **The Intent-to-Treat (ITT) Population** will consist of all participants who received either product and on whom any post-randomization efficacy information is available.
- **The Per Protocol (PP) Population** will consist of all participants who consumed at least 80% of treatment or placebo doses, do not have any major protocol violations and complete all study visits and procedures connected with measurement of the primary variable.

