#### *Removal by Qualified Investigator*

Protocol 20BWHM:

A randomized, double-blind, placebo-controlled study to investigate the effects of a *Bifidobacterium breve* strain on fat loss in healthy adults

Participant discontinuation should be considered at the discretion of the qualified investigator. The circumstances of any discontinuation must be documented in detail in the participant file and final report. If possible, the evaluations planned for the end of treatment will be carried out at the time when the participant is withdrawn from the study.

Criteria for removal of participants from the study includes:

*Clinical reasons*

A participant may be withdrawn from the study if, in the opinion of the qualified investigator, it is not in the participant's best interest to continue. Any participant who experiences a serious adverse event (SAE) may be withdrawn from the trial at the discretion of the qualified investigator. A participant will also be withdrawn due to adverse events causing clinically significant illness or the need for prohibited medication(s) during the trial. Any female participant who becomes pregnant during the course of the trial will be withdrawn and will be followed up until giving birth.

*Protocol violation*

Any participant found to have entered this study in violation of the protocol will be discontinued from the study at the discretion of the qualified investigator. This will include any participant found to have been inappropriately enrolled (did not meet eligibility criteria). Participant non-compliance includes failure to show up for study visits, failure to take the investigational product as directed, or refusal to undergo study visit procedures. Participants who are found to be taking prohibited medications or supplements without the knowledge of the qualified investigator will also be withdrawn. Any major protocol deviations (i.e. those that increase the risk to participants and/or compromise the integrity of the study or its results) will result in participant discontinuation.

*Participapnt Replacement*

For all early withdrawals, a participant leaving the study prematurely or in the event of participant removal will NOT be replaced by another. It is understood by all concerned that an excessive rate of withdrawals can render the study un-interpretable, thus unnecessary withdrawal of participants should be avoided.

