## 9.2 Run-in period – 4 weeks (Week -4 to Week -1)

Eligible participants will be contacted to undergo a 4 week (28 days) run-in period, during which they will be consuming the placebo and following an exercise intervention. Participants will come to the clinic to pick up the placebo. Compliance calls will be completed throughout the run-in period at fixed intervals.

Instructions during the run-in period:

1. Begin consuming placebo according to dosing instructions provided
2. Begin exercise regimen according to instructions provided (20 min aerobic exercise/day; 3 days/week) and record exercise in an exercise diary
3. Complete Daily Bowel Habits Diary, 3DFR and subject diary
4. Record adverse events

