### 12.2 Analysis Plan

The **Safety Population** will consist of all participants who received any amount of either product, and on whom any post-randomization safety information is available.

The **Intent-to-Treat (ITT) Population** consists of all participants who received either product and on whom any post-randomization efficacy information is available.

The **Per Protocol (PP) Population** consists of all participants who consumed at least 80% of treatment or placebo doses, do not have any major protocol violations and complete all study visits and procedures connected with measurement of the primary variable.

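### Run-in adverse events are a stated safety outcome, but participants who leave before randomization belong to no analysis set, so their events are missing from the tabulated count and denominator

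*SAP*

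**What the plan says.** The first safety outcome in SAP 2.2, and likewise in Protocol section 5, is "Incidence of pre-emergent and post-emergent adverse events". SAP 6.2 commits to a descriptive analysis of both kinds and names no population for it. Neither document defines pre-emergent.

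Randomization is at Day 0 (Protocol 8.6). Protocol 9.2 places a four-week run-in before it, during which "they will be consuming the placebo and following an exercise intervention". Participants are told to record AEs in that period, and the Schedule of Assessments (Protocol 1.3) marks AE collection at the run-in calls.

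On analysis sets, SAP 3 says: "A total of three populations are defined for all summaries and analyses".
- **Safety:** those who "received any amount of either product and on whom any post-randomization safety information is available". Protocol 12.2 has the same rule: "all participants who received any amount of either product, and on whom any post-randomization safety information is available".
- **ITT:** those who "received either product and on whom any post-randomization efficacy information is available".
- **Per protocol:** at least 80% of doses taken, no major violation, and all visits and primary-variable procedures completed.

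Protocol 12.3.2 lays out the AE frequency table by category and treatment. There and in SAP 6.1, the default denominator for categorical safety data is the study group at the visit in question.

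**The concern.** The run-in is the period in which pre-emergent events would arise, and the protocol foresees that some people will leave during it. Protocol 7.5 says: "A participant will also be withdrawn due to adverse events causing clinically significant illness". Protocol 9.4 withdraws participants who lose more than 0.7 kg per week during the run-in, and those without a stool sample within 3 days of Visit 2. Protocol 10.12 withdraws anyone below 70% exercise compliance for two consecutive weeks.

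The AE route matters most, because exclusion from the count then depends on the outcome being counted. At stake is whether a stated safety outcome describes everyone exposed to the run-in capsules and exercise, or only those who reached randomization.

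**Working it through.** **1. Can a run-in leaver enter any set?** Take a person who took run-in placebo, had an AE, and left before Day 0.

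| Set | First condition | Second condition | In the set? |
|---|---|---|---|
| Safety | Product received: arguably yes, if run-in placebo counts | Post-randomization safety information: none | No |
| ITT | Product received: arguably yes | Post-randomization efficacy information: none | No |
| Per protocol | At least 80% of doses | All visits and primary-variable procedures completed: no | No |

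For the per-protocol set, the need for post-randomization data is implied by completion rather than worded. No enrolled or run-in set exists.

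**2. Does another provision restore the count?** The AE table is by treatment, and this person has no arm. The default denominator is the study group, and this person is in none. Protocol 11.2.2 keeps some withdrawn participants in follow-up as a safety arm, but a person who was never randomized still has no post-randomization information. Protocol 7.5 and 12.3.1 put the discontinuation and its reason on record, which is a narrative or listing and not an incidence.

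**3. Is there a planned figure to reproduce?** None bears on this point. The 20% attrition in Protocol 12.1 takes 50 per group to 50 × (1 − 0.20) = 40 completers. It describes loss from the randomized groups and says nothing about run-in loss.

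**4. Direction of the effect.** Let L be the share of run-in entrants who leave, q the share of randomized participants with a run-in AE, and a the share of leavers with one.
- Reported incidence: q
- Incidence among all exposed: (1 − L)q + La
- Difference: L(a − q)

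The sign depends only on whether a is above or below q. The documents give none of the three values. The table assumes q = 10%, so the plan reports 10.0% in every cell; each cell shows the incidence among all exposed.

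| L (assumed) | a = 0% | a = 10% | a = 50% | a = 100% |
|---|---|---|---|---|
| 5% | 9.5% | 10.0% | 12.0% | 14.5% |
| 10% | 9.0% | 10.0% | 14.0% | 19.0% |
| 20% | 8.0% | 10.0% | 18.0% | 28.0% |

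With 100 randomized, these losses mean 100/(1 − L), or about 105, 111 or 125 entrants. About 5, 11 or 25 people would be in no set.

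**5. The same in counts (assumed).** Suppose 125 enter, 100 are randomized, and 15 of those 100 had a run-in AE. The plan reports 15/100 = 15%. Break-even is 0.15 × 25 = 3.75 leavers with an AE.
- 2 leavers with an AE: 17/125 = 13.6%
- 3: 18/125 = 14.4%
- 5: 20/125 = 16%
- 10: 25/125 = 20%
- 15: 30/125 = 24%

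In each case the tabulated count stays at 15 and misses the leavers' events.

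**The case against.** The strongest reply has four parts.

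- **Run-in leavers are not invisible.** SAP 6.2 ties AEs to no population and promises a description of each one. Protocol 7.5 requires the circumstances of any discontinuation in the final report, and Protocol 12.3.1 lists every premature discontinuation with its reason. This stands. A reader might infer that AEs leading to run-in withdrawal would be reported as zero; the documents do not support that. What is lost is the tabulated count and the denominator.
- **The direction is open.** A reader might infer that the percentage must be biased low. Weight loss, a missing stool sample and exercise non-compliance are exits not defined by AEs, and leavers have less time in which to have an event. This also stands, and the working shows that the sign can go either way.
- **Relevance is limited.** The run-in product is placebo for everyone, and eligibility is still being assessed at Visit 2. SAP 3 classifies only subjects who meet the eligibility criteria, so some leavers resemble screen failures. Restricting the arm comparison to randomized participants is defensible. It does not serve an outcome that covers events before randomization, in people already taking capsules and exercising.
- **Pre-emergent is undefined.** This is correct. The run-in reading is the natural one, because AEs are collected then, but the plan should state it.

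**Conclusion.** The point holds as a gap between a stated safety outcome and the sets meant to serve it. Read as written, SAP 3 and Protocol 12.2 make the tabulated pre-emergent incidence conditional on reaching randomization and having later data. Events in participants who leave before Day 0 drop out of the count. The effect on the percentage is L(a − q), which can be positive, zero or negative. Its size cannot be computed, and every percentage in the illustrations rests on assumed values. The conclusion also rests on reading pre-emergent as the run-in period.

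A reader might also infer that the randomized period would look worse than the run-in. Neither document plans a comparison of pre-emergent with post-emergent rates, so that inference has no planned analysis behind it. Post-emergent AEs by arm, the efficacy results and the sample size are unaffected. This is a minor but worthwhile correction.

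**What to change.** - **SAP 3 and Protocol 12.2:** define pre-emergent as onset from the first run-in placebo capsule up to, but not including, the first post-randomization dose. Add a run-in safety set of all participants who took at least one run-in placebo capsule, randomized or not.
- **SAP 6.2:** tabulate pre-emergent AEs on that set in one pooled column, and show separately those leading to withdrawal. Keep the existing Safety Population for post-emergent AEs by arm.

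The cost is a short addition to each document and one extra table from data already collected. The reported run-in AE rate may turn out less favourable. No treatment rule, visit or sample size changes.
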